7 OBJECTIVES AND HYPOTHESES OF THE CLINICAL INVESTIGATION

7.1 PRIMARY OBJECTIVE

The primary objective of this trial is to test the safety and efficacy of Perceval versus standard sutured stented bioprosthetic aortic valves among the intended trial population. The primary objectives will be assessed using the primary endpoint described in section 8.5.8.

7.2 SECONDARY OBJECTIVE

The main secondary objective is to compare all relevant device and subject demographics, procedural and hospital discharge, short and long term follow-up data as described in the secondary endpoints section (§ 8.5.8).

8 DESIGN OF THE CLINICAL INVESTIGATION

8.1 TRIAL TYPE

This is a prospective, randomized, stratified non blinded multi-center, international, post market trial assessed in a non-inferiority study.

The trial has a flexible sample size that will be determined adaptively. The trial will enroll up to 1234 subjects, but accrual may stop earlier at approximately 900 or 1050 subjects (see section 10.2). These subjects will be enrolled at approximately 60 worldwide investigational sites where the device is commercially available. Regardless of the sample size selected, follow up of subjects will continue annually up to 5 years. The primary endpoint will be reached at 1 year FU and, consequently, the planned primary analysis will be performed 12 months following the end of accrual.

8.2 RATIONALE FOR USE OF COMPARATORS

Aortic valve replacement is considered the gold standard for treatment of severe symptomatic aortic valve stenosis [2, 3]. For this clinical trial, the comparator will be other commercially approved standard biological sutured stented valves, both bovine and porcine. The choice of the comparator tissue valve will be at the discretion of the participating investigators. Mechanical valves required life-long anticoagulation treatment, increasing the risk of hemorrhagic and/or thromboembolic events. Thus, to avoid the introduction of a bias this prosthesis has been excluded.

8.3 PREOPERATIVE CT-SCAN

In current contemporary cardiac surgery practices, preoperative cardiac CT-scan is routinely done in the majority of cases to aid an appropriate surgical planning (including TAVI) for aortic valve replacement [2]. This standard diagnostic imaging modality allows optimal patient preparation and evaluation of anatomical characteristics such as the position of the aorta, measurement of the annulus, and presence of calcification [2]. Moreover CT-Scan will allow preoperative determination of the presence of aneurismal dilation, dissection of the ascending aortic wall, and presence of congenital bicuspid valve. All this information allows the surgeon to choose the appropriate valve size and surgical approach (i.e. appropriateness of minimally invasive approach). CT-scan will be performed in order to plan a possible mini-sternotomy in order to visualize the anatomical position of the aortic valve which will

influence the length of the mini-sternotomy (3rd or 4th intercostal space) and also the anatomical position of the aorta (midline or displaced to the right side). Detecting the presence of extensive calcification of the aorta can influence the site of aortic cross-clamping and whether a median sternotomy will be more appropriate.

For this randomized trial the included population will undergo a standard cardiac CT-scan prior to randomization. The minimum required measurement to be collected and reported are, but not limited to: aortic annulus diameter (short axis and long axis), LVOT diameter, STJ diameter, sinus of Valsalva diameter, ascending aorta diameter, aortic root height. In case of renal insufficiency a non-contrast injected CT-scan of the aorta can be performed. Standardized CT manufactured software for dimension measurement software tools can be used or generally available software like (i.e. 3-Mensio) is recommended

8.4 PREOPERATIVE AND POSTOPERATIVE NEUROLOGICAL EXAMINATIONS

8.4.1 NATIONAL INSTITUTE OF HEALTH STROKE SCALE (NIHSS)

The National Institutes of Health Stroke Scale (NIHSS) is a systematic assessment tool that provides a quantitative measure of stroke-related neurologic deficit. The NIHSS was originally designed as a research tool to measure baseline data on patients in acute stroke clinical trials. Now, the scale is also widely used as a clinical assessment tool to evaluate acuity of stroke patients, determine appropriate treatment, and predict patient outcome. The NIHSS is a 15-item neurologic examination stroke scale used to evaluate the effect of acute cerebral infarction on the levels of consciousness, language, neglect, visual-field loss, extraocular movement, motor strength, ataxia, dysarthria, and sensory loss. A trained observer rates the patient's ability to answer questions and perform activities. Ratings for each item are scored with 3 to 5 grades with 0 as normal, and there is an allowance for untestable items. A NIHSS of zero indicates a normal evaluation whereas higher numbers indicate increasing impairment and severity. Trained clinical personnel (e.g. neurologist, qualified health care professional) will be asked to determine whether there is a change in the NIHSS from the baseline discharge and up to one year visit and if this change is because a suspected stroke. The use of this score will allow a more objective assessment of the incidence of stroke as part of primary endpoint of this trial.

8.4.2 MODIFIED RANKIN SCALE

The modified Rankin Scale is a commonly used scale for measuring the degree of disability or dependence in the daily activities of people who have suffered a stroke or other causes of neurological disability. The scale runs from 0-6, running from perfect health without symptoms to death. Trained clinical personnel (e.g. neurologist, qualified health care professional) will be asked to determine the status of the patient and report the value of the scale. The use of this score will allow assessment of the grade of stroke according to the proposed guidelines [1]

8.5 SUBJECTS POPULATION

8.5.1 INTENDED POPULATIONS AND INDICATIONS IN THE PROPOSED CLINICAL INVESTIGATION

All subjects with severe symptomatic aortic stenosis or steno-insufficiency who are candidates for surgical replacement of their native aortic valve according to established guidelines [2, 3] in current medical practice and as specified in the Perceval valve IFU (Appendix 2) are the intended population for inclusion in this randomized

trial. Right mini-thoracotomy is not allowed as a surgical approach due to limited experience within the surgical community and/or suitability with the comparator standard valve.

8.5.2 INCLUSION CRITERIA

Subjects who meet all the following criteria will be included:

1. The subject has an indication for treatment by valve replacement with a bioprosthesis according to the IFU, through either full sternotomy or mini-sternotomy.
2. The subject has aortic valve disease that can be treated with a commercially available Perceval valve size, based on preoperative CT-scan.
3. The subject has:
 - a) critical aortic valve area defined as an initial aortic valve area of $\leq 1.0 \text{ cm}^2$ or aortic valve area index $< 0.6 \text{ cm}^2/\text{m}^2$

AND

 - b) Mean gradient $> 40 \text{ mmHg}$ or $V_{\text{max}} > 4 \text{ m/sec}$ by resting echocardiogram or simultaneous pressure recordings at cardiac catheterization [or with dobutamine stress, if subject has a left ventricular ejection fraction (LVEF) $< 55\%$] or velocity ratio < 0.25 ;
4. The subject is symptomatic due to aortic stenosis with functional class of NYHA II or higher.
5. The subject has signed the informed consent.
6. The subject is of legal minimum age.
7. The subject will be available for postoperative follow-up beyond one year.

8.5.3 EXCLUSION CRITERIA

Subjects who meet any of the following criteria will be excluded:

1. The subject has a contraindication for treatment by the Perceval valve or by a bioprosthetic aortic valve as stated in the IFU.
2. The subject has aneurismal dilation or dissection of the ascending aortic wall.
3. The subject is scheduled for concomitant procedures other than CABG, myectomy with or without aortic annulus enlargement
4. The subject has congenital bicuspid (i.e. Sievers type 0) or unicuspid aortic valve.
5. Anatomical structures not suitable for Perceval valve such as: aortic root enlargement, where the ratio between the diameter of the sino-tubular junction and the annulus diameter is > 1.3 .
6. The subject has a prosthetic heart valve in any position, including mitral valve repair.
7. The subject has a stroke or myocardial infarction (STEMI and NSTEMI) within 30 days prior to the planned valve implant surgery.
8. The subject has active endocarditis, myocarditis, or sepsis.
9. The subject is in cardiogenic shock manifested by low cardiac output and needing hemodynamic support.
10. The subject is allergic to nickel alloys.
11. The subject is already included in another clinical trial that could confound the results of this clinical investigation.

8.5.4 CRITERIA FOR SUBJECT RANDOMIZATION

Randomization will occur once

- a) subject has met all inclusion criteria without any exclusion criteria
- b) subject has been determined eligible for the trial through preoperative CT-scan and echocardiographic assessment,
- c) subject has received the appropriate and mandatory information about the trial,
- d) informed consent form has been obtained and signed.

8.5.5 CRITERIA FOR SUBJECT TERMINATION

All enrolled subjects will be followed until the end of the trial except upon premature discontinuation in the trial.

Participation of a subject in the trial should be discontinued when:

- The exclusion from the trial is required for the subject's safety;
- Relevant Ethics Committee and/or regulatory authority withdraw approval(s)
- The subject decides to withdraw from the trial
- The subject is deemed lost to follow up

The subject may withdraw his/her consent or cooperation (i.e. the subject refuses to participate further in the trial) at any time without jeopardizing the normal standard of care.

8.5.6 POINT OF ENROLLMENT

Subjects will be considered enrolled in the trial after all inclusion and exclusion criteria have been met and informed consent has been obtained (informed consent form dated and signed). The investigator is responsible for screening all potential subjects and selecting the ones meeting the inclusion/exclusion criteria.

All screened subjects should be recorded in a screening log, including the reason why the subjects were not deemed eligible for the trial.

For subjects who have been enrolled but who do not undergo randomization or do not undergo the protocol-required procedures, the signed informed consent and documentation must be maintained in the site files. No follow-up is needed.

Only those subjects with an assigned randomization code (through the electronic randomization process) will be included in the randomized trial.

8.5.7 RANDOMIZATION

Only subjects who have undergone standard chest CT-scan to determine if the aortic stenosis can be replaced with an available Perceval valve (size), and is potentially suitable for mini-sternotomy, may be randomized. For each subject the randomization will be performed based on the randomization list after enrollment and before valve operation, specifically after CT scan and surgical approach ("full sternotomy" or "mini-sternotomy") has been determined, to minimize bias.

Subjects will be randomly assigned in equal numbers (1:1) to one of two treatment arms. The blocked randomization list will be performed before the study start. The randomization will be stratified with 2 stratification factors, by country and by surgical approach (full sternotomy” or “mini-sternotomy”).

8.5.8 TRIAL ENDPOINTS DEFINITION AND ASSESSMENTS

The primary endpoint will be evaluated in a non-inferiority setting, with statistical hypothesis tests formally defined in section 10.

Primary endpoint

The primary endpoint is freedom from MACCE (composite endpoint of all cause death, myocardial infarction, stroke, and valve re-intervention) at one year based on CEC adjudication.

The definitions of each component endpoint are reported in the **Table 4** below, complete definitions can be found in Appendix 4.

Table 4 Definitions of the single endpoint of MACCE

Endpoint	Definition
All cause of death	Total number of deaths regardless of cause (cardiovascular mortality + non cardiovascular mortality)
Myocardial infarction	Myocardial injury as specified in VARC-2 [1]
Stroke	Stroke is defined as an acute episode of focal or global neurological dysfunction caused by the brain, spinal cord, or retinal vascular injury as a result of hemorrhage or infarction. A stroke may be classified as “undetermined” if there is insufficient information to allow the categorization as ischemic or hemorrhagic.
Valve Re-intervention	Any re-intervention, including a transcatheter valve implant, on the implanted aortic valve bioprosthesis after surgical closure of the chest.

Secondary endpoints

1. Surgical time
 - a. Cross clamp time during index procedure
 - b. Cardiopulmonary bypass time during index procedure
2. Normalized Consumption Index and reduced Normalized Consumption Index, including resource consumption items such as (but not limited to):
 - a. Operative room time,
 - b. Duration of ICU/CCU and total hospital stay
 - c. Incidence of specific serious adverse events as defined in Appendix 3
 - d. Blood transfusion(s)
3. Quality of life questionnaire
 - a. At 1 month and 1 year post surgery
4. Intraprocedural and periprocedural serious adverse events regardless of relationship with the device within 72 hours.
5. All valve and procedure relevant serious adverse events as specified in VARC-2 guidelines [1] (Appendix 7)
 - a. Early safety at 30 days
 - b. Clinical efficacy after 30 days
 - c. Time related valve safety: SVD, endocarditis, thrombosis, thromboembolic events (excluding stroke), and bleeding annually up to 5 years
6. Serious device related adverse events up to 5 years
7. Freedom from MACCE at 2, 3, 4 and 5 years of follow up
8. Pacemaker implantation and cause up to 1 year
9. Valve hemodynamics (PPM, PPG, MPG; DVI, EOA, LVOT, AI, PVL, EROA) assessed by site-reported echocardiographic parameters preoperatively, at discharge, between 1-3 month, 1 year, 3 year and 5 year.
10. Valve hemodynamics (PPM, PPG, MPG, DVI, EOA, LVOT, AI, PVL, EROA) in a reduced cohort of patients assessed by core lab echocardiographic parameters preoperatively, at discharge, between 1-3 month, 1 year, 3 year and 5 year.

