3. DOCUMENT AND CHANGE HISTORY

3.1.CHANGES IN ANALYSIS COMPARED TO CLINICAL INVESTIGATIONAL PLAN

No changes in the analysis as described in the Clinical Investigational Plan.

3.2.SAP AMENDMENT RATIONALE AND CHANGE HISTORY

Table 2 : SAP Amendment description

Version	Date	Section(s)	Description of modifications
1.0	13MAR2017		Initial Release.
2.0	26JUL2017	7,9,10,10,13	Additional general details on how to represent values in the statistical analysis. Additional specifications have been added to analysis populations (including the definition of adherence to randomization allocation). Details on compliance calculation have been added. Additional derivation rules.
3.0	28JUN2018	10, 11, 12 Editorial changes impact all the document	SAP has been amended following the CIP amendment: 
 Adaptive design; Primary analysis; Sensitivity analysis. Details on primary analysis (Bayesian approach) have been added. Additional analysis for NYHA, echocardiographic data, EQ5D. Surgical times analysis has been modified from ANOVA to ANCOVA. Editorial changes (new template per internal SOP). List of TFLs have been removed (included in a different document).
4.0	16MAY2019	12.1.2, 12.2, 12.3, 13.4	Sensitivity analyses of Surgical times have been added; Additional details for checking the assumptions for ANCOVA; Additional details have been added for the calculation and testing of NCI and rNCI, including the management of missing data (if needed) and an analysis by country; Sensitivity analyses of EQ-5D-5L have been added (using France-based scoring system and with a Mann-Whitney test); The use of a discount rate for the QALY has been removed; Additional details on calculation of EQ-VAS have been added; Details on pacemaker evaluation through ECG Core Lab have been added.

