13.1.2. Adverse Events Incidences

The incidence of AE is defined as the number of subjects with occurrence of this AE during the period of interest. The incidence rate (CIR for crude incidence rate) of an AE is defined as the number of subjects with occurrence of this AE during the period of interest divided by the total number of subjects n in the respective group (e.g., treatment group).

The incidence, incidence rate, the number of events and the percentage of events (related to the total number of events) will be summarized by AE term over the entire study post-implant period (from Day 1) and during the early and late phases (section 18.12). For the late events, the incidence rate will be calculated on the number of late patients only.

In addition, safety summaries will be done according to the following plan:

- Intraprocedural and periprocedural (within 72 hours) serious adverse events regardless of relationship with the device.

- All valve and procedure relevant (according to CEC adjudication) serious adverse event composite endpoints and their components as specified in VARC-2 guidelines (and reported in section 18.12):
 - Early safety at 30 days
 - Clinical efficacy after 30 days
 - Time related valve safety annually up to 5 years
- Serious device related (according to CEC adjudication) adverse events up to 5 years (from day 1 up to Day 1826)
- Postoperative site-reported unexpected serious adverse device effect (USADE)
- Site-reported relationship to procedure, device, drug/medication, or other Protocol Required Assessment (section 18.12)
- All late serious adverse events will be analyzed according to a constant hazard model: the linearized rates will be calculated as:
 - total number of late events divided by the total time under evaluation after 30 days (late patient-years).
 - number of patients with at least one late event divided by the total time under evaluation after 30 days (late patient-years).
- The incidence, incidence rate, the number of events and the percentage of Pacemaker (PM) implantation according to:
 - time of occurrence (overall, early, late and up to 1 year), and
 - relationship to device and procedure.

In addition, time-to-event methods (section 5.2) will be used to summarize the time to onset of the following events:

- deaths (overall, cardiovascular, and non-cardiovascular),
- explants and
- all main cardiovascular SAEs:
 - Bleeding,
 - SVD,
 - endocarditis,
 - valve thrombosis,
 - thromboembolic events,
 - stokes,

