Clinical efficacy (after 30 days)	
Serious Adverse Event (SAE):
 
YES if at least one (Time to SAE >30 days) per CEC or Echo core lab:
 
 - All-cause mortality - All stroke (disabling and nondisabling) - Requiring hospitalizations for valve-related symptoms or worsening congestive heart failure. - NYHA class III or IV (date of assessment >30 days after valve implant) - Valve-related dysfunction: 
 i. (mean aortic valve gradient ≥ 20 mm Hg, EOA ≤ 0.9–1.1 cm² and/or DVI < 0.35 m/s, AND/OR ii. moderate or severe prosthetic valve regurgitation) 
NO, otherwise

Derived variable	Derivation algorithm
Time-related valve safety	
Serious Adverse Event (SAE):
 
YES if at least one (Time to SAE >30 days) per CEC or echo core lab:
 
 - Structural valve deterioration (both points i. and ii. have to be met): 
 i. Valve-related dysfunction: 
 ▪ mean aortic valve gradient ≥ 20 mm Hg, EOA ≤ 0.9(if BSA<1.6 cm²) or 1.1(if BSA≥ 1.6 cm²) cm² and/or DVI<0.35 m/s, AND/OR ▪ moderate or severe prosthetic valve regurgitation) ii. Requiring repeat procedure (TAVI or SAVR) - Prosthetic valve endocarditis - Prosthetic valve thrombosis - Thrombo-embolic event, non-cerebral , - TIA - STROKE - VARC bleeding (BARC type 5, BARC type 3A, 3B and 3C, BARC type 2), unless clearly unrelated to valve therapy (e.g., trauma) : Device and/or procedure related 
NO, otherwise

MACCE (Yes/No)	
Serious Adverse Event (SAE), Valve re-intervention:
 
YES if at least one per CEC:
 
 - Death - Myocardial infarction - Stroke - Reintervention 
NO, otherwise

Derived variable	Derivation algorithm
MACCE @ 1 year (Yes/No)	
Serious Adverse Event (SAE), Valve re-intervention:
 
YES if at least one per CEC:
 
 - Death (Time to SAE <=365 days) - Myocardial infarction (Time to SAE <=365 days) per CEC - Stroke (Time to SAE <=365 days) per CEC - Reintervention (Time to SAE <=365 days) 
NO, otherwise

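### SAP Table 8 counts stroke in time-related valve safety, although the protocol defines that endpoint without stroke, and the difference is not declared

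*Protocol*

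**What the plan says.** Protocol section 8.5.8 lists, as secondary endpoint 5c, "Time related valve safety: SVD, endocarditis, thrombosis, thromboembolic events (excluding stroke), and bleeding annually up to 5 years". The synopsis defines it the same way, ending in "thromboembolic events (excluding stroke), and bleeding annually up to 5 years". The parent item, endpoint 5, reads "All valve and procedure relevant serious adverse events as specified in VARC-2 guidelines [1] (Appendix 7".

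SAP section 18.12, Table 8, derives a variable of the same name. It is set to yes if at least one listed event occurs more than 30 days after implant, as judged by the CEC or the echo core lab. The list holds structural valve deterioration, endocarditis, valve thrombosis, "Thrombo-embolic event, non-cerebral", then TIA and STROKE as separate entries, then bleeding.

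SAP section 13.1.2 plans summaries of the "composite endpoints and their components as specified in VARC-2 guidelines (and reported in section 18.12", so Table 8 governs what is reported.

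On departures from the protocol, SAP section 3.1 says: "No changes in the analysis as described in the Clinical Investigational Plan". The version 5.0 entry in SAP section 3.2 names section 18.12 but says only that derivations were updated. Protocol section 10.6 requires a relevant analysis change to be made by amendment, or to be set out with its rationale in a dedicated section of the SAP.

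**The concern.** The two documents give one endpoint two contents, and the difference is a named event: the protocol takes stroke out and the SAP counts it. The SAP is what gets programmed, so the protocol's composite would not appear in the report.

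Stroke is already part of the primary MACCE endpoint and of the SAP's early-safety and clinical-efficacy composites. As the protocol defines it, 5c is the only one of the three VARC-2 groupings under endpoint 5 with a stated stroke exclusion. Adding stroke lets an imbalance in stroke show up as an imbalance in time-related valve safety. A reader relying on the protocol's definition would not know this, because the SAP says nothing has changed.

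**Working it through.** The plan states no figure for this endpoint, so there is none to reproduce. The check is a comparison of texts, followed by simple arithmetic for size.

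**Comparison of components**

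| Component | Protocol 5c | SAP Table 8 |
|---|---|---|
| Structural valve deterioration | included | included |
| Endocarditis | included | included |
| Valve thrombosis | included | included |
| Thromboembolic event, non-cerebral | included | included |
| TIA | not named, not excluded | listed |
| Stroke | excluded | listed |
| Bleeding | included | included |

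1. Stroke is a direct conflict: one text excludes it and the other counts it.
2. TIA is not. The protocol's parenthesis removes only stroke, and a TIA can be read as a thromboembolic event other than stroke. Listing it is compatible with 5c; the protocol simply does not say how it is classed.
3. The conflict reaches the output, because SAP 13.1.2 points to section 18.12.
4. It is undeclared. SAP 3.1 reports no change and the version 5.0 log mentions neither stroke nor a reason, so neither route in protocol 10.6 has been followed.

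**Size**

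Inputs:
- Late stroke rate of 0.8%, from the pooled earlier Perceval trials (protocol section 6.2). The late rate is used because Table 8 counts only events after day 30; the 1.2% early rate falls outside that window.
- Total sample size of 900, 1050 or 1234, randomized 1:1 (protocol sections 8.5.7 and 10.2), giving 450, 525 or 617 per arm.

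Formula: subjects per arm who could enter through stroke = n per arm × 0.008.

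| N | n per arm | Calculation | Subjects per arm |
|---|---|---|---|
| 900 | 450 | 450 × 0.008 | 3.6 |
| 1050 | 525 | 525 × 0.008 | 4.2 |
| 1234 | 617 | 617 × 0.008 | 4.9 |

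These are ceilings at that rate. A subject with a stroke who also has another component, such as a qualifying bleed, is counted already. The documents give no TIA rate, so no figure is attached to TIA.

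**The case against.** Four arguments can be made for the SAP.

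**The detail was delegated.** Protocol section 10.1.5 leaves the definition of secondary analyses to the SAP, and the SAP is itself a pre-specified document. This stands to the extent that the composite cannot be called unplanned. It does not cover silently reversing an exclusion that the protocol states twice, since section 10.6 asks for such a change to be declared.

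**VARC-2 may explain the SAP list.** Both the parent heading of endpoint 5 and SAP 13.1.2 cite it. The content of protocol Appendix 7 is not reproduced, so this cannot be checked. Whatever it contains, the protocol's own wording for 5c excludes stroke.

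**The consequences are limited.** SAP section 13 describes safety data by arm, with no test or claim attached to this composite. Components are reported with it, and stroke has its own time-to-event summary. A difference driven by stroke would therefore be visible. This stands and is the main reason the point is minor, but the composite as the protocol defines it would still be missing.

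**The two arms may be affected alike.** If late stroke rates are similar, the expected difference between arms moves little. This also stands; the level of the composite still changes.

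**Conclusion.** The point holds for stroke. SAP Table 8 includes it, protocol 5c excludes it, and the SAP declares no change. Following the SAP gives a composite that is not the one specified in the protocol.

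The effect is confined to one descriptive secondary safety composite. The ceiling of about 3.6 to 4.9 subjects per arm assumes that the pooled 0.8% is a cumulative proportion, that it applies in both arms, and that its late period corresponds to events after day 30. Section 6.2 gives no follow-up duration for that rate, so the number over the five years planned here could differ. The primary MACCE analysis, alpha and power are unaffected.

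Three stronger readings are tempting but unsupported:
- That TIA is a second contradiction. The protocol does not exclude it.
- That stroke would be a main driver of the composite. The documents give no late rate for bleeding or TIA. Setting 0.8% beside the 1.4% endocarditis rate of one earlier trial compares a late pooled rate with a one-year rate in a different cohort, and ignores overlap between components.
- That the protocol left stroke out for a considered reason. No section explains the exclusion.

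**What to change.** In SAP Table 8, take STROKE out of the time-related valve safety derivation so that the reported composite matches protocol 5c. State in the same row whether TIA counts as a thromboembolic event. If a version that includes stroke is also wanted, show it as a second, clearly labelled row and record the change with its rationale in SAP section 3.1, as protocol section 10.6 requires.

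The cost is one table edit, or one extra output row and a sentence in section 3.1. No new data are needed, and no information on stroke is lost, because stroke stays in MACCE and in its separate time-to-event summary.
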